Older obese adults suffer disproportionately from walking mobility limitations. Sedentary, obese older adults are at an increased risk for having or developing difficulties with mobility. These individuals are often excluded from studies due to their advanced mobility limitations. A number of studies have compared the effects of weight loss alone, exercise alone, or weight loss in combination with exercise on functional performance in older adults, but none of the studies have specifically targeted subjects who use walking assistive devices. The purpose of this study is to test the effects of a 3 month multi-modal balance intervention (MMBI) with a nutrition program with optional retention till 24 months on fitness, functional performance, mobility, and muscle mass. The results of this study will lead to new and more effective interventions that could reduce disability, fall risk, injury-related hospitalization and death in older Veterans.

ID: VIEW4E02805CF7000
Name: v2_Lay Summary

Justification, Objective, & Research Design

If you uploaded a separate research protocol document in the 'Research Protocol' page, cite the applicable section and page numbers from that document in the answer boxes below.

- 1 *** Describe the purpose, specific aims, or objectives of this research. State the hypothesis to be tested:**
 Specific aim 1: Examine the effects nutrition + multimodal balance intervention (MMBI) on mobility and functional performance in the following outcomes:
 a. 6 minute walk (primary outcome)
 b. Other physical performance outcomes: 6MW with economy of gait, gait rite, four square step test, 8 foot up and go, short physical performance battery, grip strength, lower extremity strength
 Specific aim 2: Examine the relationship between muscle mass, strength, and functional performance using DXA and CT scans to quantify body composition.
 Specific aim 3: Examine the impact of the intervention on patient reported measures of function and disability using the Late Life Function and Disability Instrument (LLFDI).
- 2 *** Discuss the research design including but not limited to such issues as: probability of group assignment, potential for subject to be randomized to placebo group, use of control subjects, etc.:**
 All subjects will now receive MMBI and nutrition (combined intervention). Weight loss will be a covariate in the analyses.
- 3 *** Describe the relevant prior experience and gaps in current knowledge. Describe any relevant preliminary data:**

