PHASE 1 SCREENING will occur following written informed consent and will include medical history and physical examination will be performed at the Baltimore VA Medical Center Geriatrics Research Education and Clinical Center (GRECC). Individuals who have a history of symptomatic angina or claudication, or who are otherwise unable to complete the 6 minute walk test will not be eligible and will exit from the study. Gait speed (to determine study eligibility) will be assessed during a 10 meter walk. Subjects will be assessed for the appropriateness, fit, and use of walking mobility aids. Disability will be assessed through administration of the 6 item activities of daily living (ADL) and 6 item instrumental activities of daily living (IADL) questionnaire. A blood draw will be completed to assess their ability to safely participate in the study. Participants who meet inclusion/exclusion criteria will proceed to baseline testing. We anticipate that 20-30% of the individuals brought in for screening evaluations will not qualify for this study. Participants who meet inclusion/exclusion criteria will proceed to Phase 2. If new medical abnormalities are detected during research procedures we will tell the participants of the results and with their permission, we will forward the results to their primary care physician for appropriate follow up. For VAMHCS patients, lab results will be listed in their electronic medical record (CPRS). For those Veterans who do not receive care at the VAMHCS, they will be provided copies of their results, and with their permission, we can share with their non-VA provider. For subjects enrolled in this study before the COVID-19 pandemic that we are inviting back into the study we will review their medical history and medications before they resume participation in the study.

Phase 2 BASELINE TESTING includes:

Body composition assessment (see below for description)
 Anthropometric measurements (see below for description)
 Lateral mobility and balance assessments (see below for description)
 Patient reported perceptions of function and disability (Late-Life Function and Disability Instrument questionnaire)
 Physical Function test battery (see below for description)
 Self reported physical activity levels (CHAMPS questionnaire)
 Assessment of cognitive function (Montreal Cognitive Assessment, MoCA)
 3 x 24 hour food records

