 The order of the tests will vary from subject to subject depending upon their schedule and the availability of the equipment.

After completion of baseline testing, participants will enter the intervention phase

Phases 3-5. Interventions and Outcome Assessments will be performed at 3 months and at 6, 12 months and a final assessment at the end of 24 months for subjects who are in the optional retention exercise program.

INTERVENTIONS

MULTIMODAL BALANCE INTERVENTION (MMBI): The MMBI has been designed to specifically address the proximal strength, balance, and mobility deficits of these severely deconditioned older obese Veterans who use assistive devices. The MMBI intervention will be conducted in the VA hospital or the VA Annex in downtown Baltimore and at the more suburban Loch Raven Community Based Outpatient Clinic. The two sites are 6 miles apart and there is routine shuttle service between them. Our MMBI will be held once a week or once every other week for an hour and will consist of a dynamic balance class (30 minutes), a supervised obstacle course (10 minutes), and lower extremity and core strengthening (20 minutes). The exercises will focus on dynamic weight shifts with an emphasis on the lateral and diagonal directions. Over time the exercises will gradually increase in difficulty. An instructor will lead each class and 1-2 assistants will be present to assist in mitigating the risk of falls. The supervised obstacle course will focus on obstacle negotiation, walking over challenging surfaces, and moving in the lateral, diagonal, and backward directions. Strength training of the lower extremities and core will focus on strengthening the major muscles of the lower extremity and core (hip flexors/extensors, hip abductors/adductors, knee flexor/extensors, ankle planter flexor/dorsiflexors, ankle invertors/evertors, and core abdominal/back extensor muscles) utilizing commonly standard gymnasium equipment, ankle weights, and body weight. If group exercise is unavailable due to COVID-19, individuals will be provided with a written home exercise program to perform or sessions via telehealth twice a week. The intervention is 3 months long with optional extension out to two years.

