
We have developed a nutrition class curriculum, based on the principles and techniques of the VA MOVE! Program which focuses on nutrition education, portion control, and other weight management skills. The classes include behavior modification and cooking demonstrations. Spouses, caregivers, and significant others who are involved in shopping and meal preparation will be encouraged to attend along with the research subject. Sample menus using the exchange meal planning principles from the ADA will be provided. We have found it valuable to have a "lunch bunch" food session where the dietitians can observe dentition, social interaction among subjects while they eat, as well as whether they have any difficult feeding themselves. Participants will receive a course outline, a weight table, and weekly food suggestions, emphasizing easy to assemble meals and snacks. They will be asked to keep weight and food diaries to monitor their progress and adherence. Individual dietary recommendations, i.e. personalized food plans, will be developed based on the participant's preferences. Each subject's daily caloric intake will be designed to produce a 10% weight loss over the first 6 months of the study. Subjects with, or at risk of having, sarcopenic obesity, the energy deficit will be more moderate than usual (range of 200-500 kcal/day) with emphasis on a higher intake of proteins of high biological quality (up to 1.5 g/kg). Based on current recommendations of the American Geriatrics Society, all subjects will be advised to take over the counter supplements of at least 1000 units of vitamin D per day and 1200 mg of calcium. We have successfully employed this nutritional intervention in GRECC studies for >25 years.

STUDY OUTCOME MEASURES will be performed at baseline and after 3 months, and at 6, and 12 months of intervention for subjects who into the longer intervention. .

Physical Function tests include include the primary outcome of distance walked on the 6-minute walk test

a) Six-minute walk test: Participants are instructed to "cover as much distance as they can" over a flat 100 foot walking surface demarcated by traffic cones.
 b) 6 minute walk test with measurement of economy of gait: participants complete the 6 minute walk wearing a portable metabolic monitoring equipment (Cosmed K4b2, Cosmed, Rome, Italy) worn on the chest to assess energy expenditure during overground walking.

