Performance-based tests: 6MWD, 6MWD with economy of gait measurement, SPPB, handgrip strength, FSST, and FGA test: the FSST and the FGA test are timed tests that assess the dynamic ability to change directions while walking or stepping. The ability to negotiate stepping over obstacles (in the FSST and FGA) allows for the examination of real life walking and stepping skills. The SPPB involves tests of balance, gait and proximal lower body strength. All of these tests are found to be valid and reliable measures in older adults. No tests will be performed before the subject is examined by a physician and following verification of the absence of exclusion criteria (which would potentially preclude safe administration of physical function testing). These tests will be performed at the Baltimore VA Medical Center and/or at the BVAMC Annex located at [name], 4 blocks from the BVAMC and/or the Loch Raven Robotics and Rehab building at [name]. The testing location will be dependent upon the patient's schedule and schedule of the research staff. These tests involve a variety of timed walks, getting up from a chair, and tests of balance. There is a small risk that patients will fall, get chest pain, short of breath or become dizzy during these tests. Patients will stop the test if there are any untoward symptoms such as chest pain. There is a small risk of muscle strain or pulled muscles in the measurement of strength and fatigue. We have performed >1000 tests of functional performance without complication. To minimize risk to patients an exercise technician who is trained in CPR will be administering these tests. A crash cart and emergency medications are available in the area where these tests are performed at the BVAMC. For tests performed at the Annex, a clinical provider is present to supervise these sessions and available for consult in case of any problems. If there is a medical emergency, an AED is available on site and the 911 emergency medical system would be activated by the research team. We believe that it is highly unlikely that a subject will develop a medical emergency that would require the 911 system to be activated because in more than 25 years of training more than 1000 research subjects we have never had a subject who needed emergency treatment during tests of physical performance. The use of the QTug during these tests does not add any known risk.

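### Practice before the baseline 6-minute walk is not standardised or measured, so in this single-arm before-after trial any learning that remains after baseline is counted as treatment effect

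*Combined protocol and SAP*

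**What the plan says.** All places are in the combined protocol and SAP.

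- **Design** (Justification, Objective, & Research Design, item 2): "All subjects will now receive MMBI and nutrition (combined intervention"). The same item adds that "Weight loss will be a covariate in the analyses". No other covariate is named there.
- **Primary outcome and analysis** (same section, item 1; Sample Size and Data Analysis, item 2): distance on the 6-minute walk is primary. Aim 1 is analysed by repeated measures ANOVA over time.
- **Phase 1 screening** (Study Procedures, item 1): people with symptomatic angina or claudication, or "otherwise unable to complete the 6 minute walk test will not be eligible and will exit from the study". The only walk that this paragraph expressly schedules is a different one: "Gait speed (to determine study eligibility) will be assessed during a 10 meter walk".
- **Eligibility list** (Eligibility, item 1.2): it contains no 6-minute walk item.
- **Timing of performance tests, including the 6-minute walk** (Research Related Risks, item 1): "No tests will be performed before the subject is examined by a physician and following verification of the absence of exclusion criteria".
- **Phase 2 baseline** (Study Procedures, item 1): the physical function battery contains the standard 6-minute walk. It also contains a second version in which "participants complete the 6 minute walk wearing a portable metabolic monitoring equipment".
- **Order** (Study Procedures, item 1): "The order of the tests will vary from subject to subject depending upon their schedule and the availability of the equipment".

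The plan describes no practice walk, duplicate baseline or run-in, and no analysis that separates familiarisation from treatment.

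**The concern.** With every participant treated, the mean change from baseline is the sum of treatment effect, learning on the test and natural variation. Two things follow.

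First, the baseline walk does not mean the same thing for everyone. One participant may reach it with no earlier walk, another after a Phase 1 walk, and another after the metabolic walk in the same battery. Two further routes to unequal practice are documented. Recruitment draws on GeroFit, a programme whose reported results include 6-minute walk distance. People enrolled before the pandemic are invited back and may have walked the test already.

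Second, whatever learning remains after baseline enters the 3-month change. No planned pre-treatment repeat under the same conditions could show whether it is small or large. At stake is whether a gain near the plan's own threshold for meaningful change can be attributed to the intervention.

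**Working it through.** **Inputs from the plan (Sample Size and Data Analysis, item 1).** Planning effect 30 m with SD 50 m; two-sided alpha 0.05; power 0.80; 45 per group; 60 enrolled, attrition 20-25%, 45 completers; meaningful change 19-22 m; pilot change 57 m with SD 60 m.

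**Assumed, because the documents give no figure.** Learning that remains after baseline: 5-20 m. SD of the difference between two untreated walks: 20-40 m.

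**1. The plan's own figure.** A two-sample t-test for 30 m with SD 50 m needs 45 per group (power 0.804), or 44 by normal approximation. So 45 reproduces, but as a comparison of two groups. The 30 m is likewise described as an advantage over exercise alone. It serves below only as a yardstick. Completers: 60 x 0.75 = 45.

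**2. Learning against the plan's yardsticks.**
- Against 30 m: 5/30 = 17%; 20/30 = 67%.
- Against 19-22 m: 5/22 = 23%; 20/19 = 105%.

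**3. What learning alone could do to the test.** As a simplification of the repeated measures model, take a two-sided one-sample t-test on change in 45 completers.
- Smallest significant mean change = 2.015 x SD/sqrt(45): 15.0 m for SD 50 and 18.0 m for SD 60.
- Chance of a significant change when the true treatment effect is zero:

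| Learning after baseline (assumed) | SD 50 m | SD 60 m |
|---|---|---|
| 5 m | 0.10 | 0.09 |
| 10 m | 0.26 | 0.19 |
| 15 m | 0.50 | 0.38 |
| 20 m | 0.75 | 0.59 |

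The nominal rate is 0.05. These figures show sensitivity to an assumption; they do not estimate the bias in this trial.

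**4. What a recorded Phase 1 walk would show.** Both walks precede attrition, so about 60 people contribute, taking the 60 in the sample size section as those who reach baseline. The 95% half-width for the mean Phase 1 to Phase 2 change is 2.001 x SD/sqrt(60):
- SD 20: 2.001 x 20/7.746 = 5.2 m
- SD 40: 2.001 x 40/7.746 = 10.3 m

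**5. Why the practice change should not be subtracted.** The contrast (follow-up minus baseline) minus (baseline minus Phase 1) has variance 1 + 4 + 1 = 6 units of single-walk error, against 2 for simple change, if errors are equal and independent. The SD rises by sqrt(3), from 50 to 86.6 m. With 45 completers, power for 30 m falls from 0.976 to 0.62.

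**6. Why the longer of two walks is a poor baseline.** With no learning and normal errors, the longer of two walks exceeds a single walk on average by SD/sqrt(2 x pi) = 0.399 x SD of the difference. That is 8 m for SD 20 and 16 m for SD 40. Set against a single follow-up walk, it would shrink the gain even if nobody learned anything.

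**The case against.** The strongest reply is that the documents are silent, which is weaker than showing that data are thrown away. A reader might infer that Phase 1 requires a 6-minute walk whose result is discarded. The text does not support that. It excludes people unable to complete the test, expressly schedules only the 10-metre walk, and does not list the 6-minute walk among the eligibility criteria. Staff could apply the rule to a Phase 1 walk, to the Phase 2 walk, or from history. This objection stands, and the point rests on the ambiguity alone.

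A reader might also infer that all familiarisation counts as treatment effect. If a Phase 1 walk is done, baseline is already a second walk and the first practice gain precedes it. Only the remaining learning enters the primary change. That also stands.

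Nor would a Phase 1 walk be the only pre-treatment repeat, since the metabolic walk is another. Its conditions differ and its order is not fixed, so it is not a clean check. It is, however, a further source of unequal practice.

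Finally, a short gap between Phase 1 and Phase 2 says nothing about drift over three months, and the gain from a first to a second walk need not equal that from a second to a third. This limits what the added walk can show. It does not remove the value of knowing whether short-term practice is small or large.

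**Conclusion.** The point holds in a limited form. The plan leaves practice before the baseline walk free to vary between participants, and it has no internal check on learning that continues after baseline. In a single-arm trial that learning is counted as treatment effect. Its size is unknown: an assumed 5-20 m would be 17-67% of the 30 m planning effect and about a quarter to all of the 19-22 m meaningful change.

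The documents do not support the stronger claims that a required screening walk is discarded, that every metre of familiarisation is counted as benefit, or that a second pre-treatment walk could stand in for a control group. The conclusion rests on the absence of any stated rule for the Phase 1 walk, on the unfixed test order, and on learning of the assumed size. If learning after baseline is negligible, the primary result is little affected, but the trial as planned could not show that.

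**What to change.** 1. State that every participant completes the eligibility 6-minute walk in Phase 1, after the physician examination and the check for exclusion criteria and before the Phase 2 battery, and that the distance is recorded. The 6-minute walk is not on the exclusion list, so this order fits the existing safety text. A separate day need not be required, but report the interval between the two walks.
2. Keep the Phase 2 standard walk as baseline for the primary analysis.
3. Do the standard walk before the metabolic walk at every assessment.
4. Report the mean Phase 1 to Phase 2 change with its 95% CI beside the primary change. Describe it as a check on short-term practice, not as a control for three-month drift, and do not subtract it.
5. Do not use the longer of the two walks as a sensitivity baseline. If one is wanted, use their mean. It lacks the built-in upward bias, though any learning between the walks would pull it below the Phase 2 value, so it reduces noise without removing practice.

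Cost: one data field, and one six-minute walk for anyone who would not otherwise walk in Phase 1. The sample size does not change. The reported practice change may make the gain look less favourable.

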We anticipate that some participants will have acute medical events during the study and may need to curtail or temporarily suspend the exercise intervention. When this occurs, the participant's status will be changed to 'suspended'. When medically cleared, we will perform a modified re-initiation of the training phase until the participant can re-establish exercise intensity previously performed, at which time they will resume the study at the week at which they were assigned suspended status. If an acute medical event occurs in the 2 weeks prior to the planned interim or final month outcome assessment, we will postpone the assessment until at least 6 thrice-weekly in-center training sessions can be completed at target exercise intensity. Participants who are on medical hold for more than 4 concurrent weeks will be evaluated on an individualized basis by the site PI to assess their appropriateness to return to intervention activities.

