2 * Provide the plan for data analysis. Include in the description the types of comparisons that are planned (e.g., comparison of means, comparison of proportions, regressions, analysis of variance, etc.), which is the primary comparison/analysis, and how the analyses proposed will relate to the primary purposes of the study:

All comparisons of primary and secondary outcomes will be performed in accordance with intention-to-treat principles. As with all clinical trials, it is anticipated that there may be missing data elements. Multiple imputation will be used to account for missing values. Our first analyses will be exploratory designed to identify extreme values. Extreme values will be checked to make sure they are not the result of data entry errors. Statistical significant will be a two-sided alpha of 0.05.

Specific aim 1. Our study will compare the effects of MMBI+nutrition on mobility and functional performance in older obese Veterans with walking impairment requiring a walking assistive device. We will use repeated measures ANOVA to model the time-course of our outcome measures. We will use AICC (a modification of Akaike's Information Criterion) to choose between three covariance structures that can account for the serial auto-correlation of our subject's data.

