Specific aim 2. Using DXA and CT scans, we will quantify total muscle mass and cross-sectional muscle area at numerous levels at baseline, 3, 6, 12, and 24 months. At baseline there should be a direct correlation between total muscle, ASMI, cross-sectional muscle mass and the indices of functional performance. With the exercise intervention, we expect that there will be small, but significant increases in lean muscle mass and ASMI (ANOVA). This change may be beyond the limits of detection of the DXA. Assessment of cross-sectional muscle area by CT scan may provide a more sensitive measurement of muscle mass than DXA. The relationship between muscle mass, strength, and functional performance at baseline and after the intervention will be examined. Body composition (% fat, fat-free mass, regional distribution of body fat) may change with intervention. Regression analyses will be used to determine whether the change in 6MWD, and other mobility parameters are related to the change in muscle mass (DXA, CT scan) or muscle strength (Biodex) with intervention. We will also perform multivariate modeling. It is important to dissect how much of the improvement in mobility after intervention is attributable to changes in fitness, economy of gait, and other factors such as balance, and strength. The functional measures in combination with the assessments of muscle mass by DXA will also allow us to determine the prevalence of sarcopenia using recently published NIH guidelines.

Specific Aim 3. We will examine the impact of the intervention on patient reported measures of function and disability using the LLFDI. We will compare LLFDI total scores and subscale scores using an analysis plan similar to that for aim 1. We will also examine the correlations between the self-reported measures and performance measures to provide further evidence of validity and reliability.

ID: VIEW4E02806052800
Name: v2_Sample Size and Data Analysis

Sharing of Results

1 * Describe whether results (study results or individual subject results, such as results of investigational diagnostic tests, genetic tests, or incidental findings) will be shared with subjects or others (e.g., the subject's primary care physicians) and if so, describe how it will be shared:
Results which have clinical relevance will be shared with participants, and with their permission, their primary care providers.

ID: VIEW4E02808CBD800
Name: v2_Sharing of Results

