A mini-mental status examination will be performed as part of the history and physical examination to screen for dementia. Patients with MMSE <24 will be excluded. The research subject will be provided with a copy of all forms and copies of the signed forms will be placed in the patient's research chart and in the investigators files..

The informed consent process will be documented in the participant's study record and their VA clinical chart.

In order to ensure continued consent and understanding of the study procedures, participants may, at any time point, ask research staff to review individual study procedures and any pre-procedure preparation they will need to do.

Subjects enrolled in this study before the COVID-19 pandemic that we are inviting back into the study will be reconsented.

3 * Confirm that the consent process will explain the following:

- The activities involve research.
- The procedures to be performed.
- That participation is voluntary.
- The name and contact information for the investigator.

Yes No

4 * Describe who will obtain Informed Consent:

The PI, co-investigators and/or research team.

5 * If obtaining consent from a legally authorized representative (LAR), describe how you will confirm that the individual is the LAR and can provide legally effective informed consent. (Answer "N/A" if not obtaining consent from LARs)

N/A

6 * Describe the setting for consent:

In private rooms free of distractions and onlookers/passers-by and to ensure privacy at the BVAMC Geriatric Research and Education Clinical Center, or at the Baltimore VA Annex, or at the Loch Raven Robotics and Rehab Building.

7 * Describe the provisions for assessing participant understanding:

A mini-mental status examination will be performed as part of the history and physical examination to screen for cognitive dysfunction. Patients with MMSE <24 will be excluded.

8 * Describe the consideration for ongoing consent:

Subjects will need to come to the gym for ongoing participation in the study. Their voluntary arrival to the site is strong evidence of their ongoing consent.

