- 4 If the research involves using identifiable private information or identifiable biospecimens, please explain why the research could not practicably be carried out without using such information or biospecimens in an identifiable format.
- 5 In some cases there will be additional pertinent information during the study that should be given to the participating subjects. For those subjects who have not been given informed consent because there is a waiver or alteration of the consent process, explain how the subjects will receive this additional important information. If applicable, please explain why a subject would not receive additional pertinent information.
N/A. Individuals who would be eligible to take part in the study will be given the opportunity to agree and sign the informed consent document or to decline participation.
- 6 If you are requesting an alteration of the consent process please explain why this request is necessary for the conduct of the research study. Please identify specifically what is being altered or changed in the consent process.
N/A

ID: VIEW/E1C73B344800
Name: v2_Waiver/Alteration of Consent Process

Consent and HIPAA Authorization Forms - Draft

1 Upload all of your Consent Forms for approval. Use only Microsoft Word.

Name	Created	Modified Date
VA Unapproved Consent Version02272021.doc(0.01)	3/11/2021 2:50 PM	3/11/2021 2:50 PM

IMPORTANT NOTE: the above list of consent forms (if any) are DRAFT versions. Under no circumstances should copies of these be distributed to patients/study subjects. If/when this research submission is approved by the IRB, approved consent forms will be available for download and use from the "Documents" tab of the Submission's workspace (click Exit and then look for the Documents tab - approved submissions only)

1A Archived Consent Forms:

Name	Created	Modified Date
VA Consent Version 6 3.12.20_clean.doc(0.02)	9/16/2019 3:59 PM	3/12/2020 11:48 AM
VA Consent Version 11.8.18(0.02)	8/23/2018 10:58 AM	11/8/2018 1:12 PM
VA Unapproved Consent Version 4- 11.15.17(0.04)	10/10/2017 11:05 AM	11/15/2017 2:06 PM
VA Unapproved Consent Version 4 tracked changes- 11.2.17.doc(0.03)	10/10/2017 11:05 AM	11/2/2017 1:47 PM
VA Unapproved Consent Version 3- 7.7.17(0.01)	7/7/2017 8:47 AM	7/7/2017 8:47 AM
VA Unapproved Consent Version 3- 7.7.17 tracked changes(0.01)	7/7/2017 8:47 AM	7/7/2017 8:47 AM
va unapproved consent from version 2 track changes(0.01)	2/1/2017 8:26 AM	2/1/2017 8:26 AM

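### Does the plan need to fix which baseline applies to people enrolled before the pandemic and invited back?

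*Combined protocol and SAP*

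**What the plan says.** **Return to the study.** Study Procedures, item 1 (Phase 1 Screening) says of people enrolled before the pandemic and invited back that "we will review their medical history and medications before they resume participation in the study". Informed Consent Process, item 2 adds: "Subjects enrolled in this study before the COVID-19 pandemic that we are inviting back into the study will be reconsented".

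**Usual sequence.** The same Phase 1 text says "Participants who meet inclusion/exclusion criteria will proceed to Phase 2", which is baseline testing. Study Procedures then continues: "After completion of baseline testing, participants will enter the intervention phase". Under Study Outcome Measures, follow-up visits are indexed by months of intervention.

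**Pauses.** Study Procedures has a suspended status for acute medical events. After medical clearance and a modified re-start of training, participants regain their former exercise intensity, "at which time they will resume the study at the week at which they were assigned suspended status". Medical holds longer than 4 weeks are assessed case by case by the site investigator.

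**Analysis.** Sample Size and Data Analysis, item 2 calls for intention-to-treat, with multiple imputation of missing values. For aim 1: "We will use repeated measures ANOVA to model the time-course of our outcome measures". For aim 2: "Regression analyses will be used to determine whether the change in 6MWD, and other mobility parameters are related to the change in muscle mass" (or muscle strength). Neither aim mentions returners. Under Justification, Objective, & Research Design, item 2, everyone now receives exercise plus nutrition.

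**The concern.** Two baselines seem possible for a returner. Re-consent, and the place of the sentence within Phase 1, suggest that the person goes through baseline testing again. The word resume suggests that the pre-pandemic baseline stands, and the suspended-status rule appears to support that by returning a paused person to the week at which they stopped.

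The choice matters more than it would in a randomised comparison, because no concurrent control group absorbs change during the pause. For someone who stopped before month 3, the pre-pandemic baseline makes the 3-month change cover the programme plus the pause, while a re-entry baseline covers the programme alone. If both walks exist and no rule is written, the choice could be made after both are seen. The aim 2 regressions also need walk change and muscle change measured from the same visit.

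**Working it through.** **1. Is there a contradiction?** The three texts have different scopes.

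- Phase 1 and the consent section cover people enrolled before the pandemic. They require re-consent and a review of history and medications. They neither order nor exclude repeat baseline tests.
- The suspended-status rule is triggered by an acute medical event and does not mention the pandemic. Even by analogy it would not return people automatically to the same week, because holds over 4 weeks go to individual assessment. A pandemic pause would be far longer: the consent files dated 12 March 2020 and 27 February 2021 are 352 days, or 352/7 = 50.3 weeks, apart. These are file dates, not visit dates, so they are only a guide.
- The analysis section covers everyone and is silent on returners.

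No two rules give the same person different instructions. What remains is a missing detail.

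**2. Who is affected?** Someone who completed month 3 before the pause already has a baseline and month-3 pair, so their 3-month change does not depend on this question. Only those who paused before month 3 are affected.

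**3. How much time is at issue?** Assume a pause of 26 to 52 weeks. From the pre-pandemic baseline, the month-3 change spans 13 + 26 = 39 to 13 + 52 = 65 weeks, of which the pause is 26/39 = 67% to 52/65 = 80%. From a re-entry baseline it spans 13 weeks. The pause was not necessarily idle: Study Procedures provides a home programme or telehealth sessions when group exercise is unavailable because of COVID-19.

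**4. Is the planned sample size affected?** For a 30 m difference with SD 50 m, two-sided alpha 0.05 and power 0.80, a two-sample t-test needs 44.6, so 45 per group, as stated. A paired test would need 24. With 25% attrition, 45/0.75 = 60, the stated enrolment. None of this depends on the baseline rule.

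**5. How far could the result move?** The shift in the mean is f × d, where f is the affected share of those analysed and d is the difference between the two candidate baselines. The documents give neither.

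- Per person among 45 completers: 30/45 = 0.67 m; 50/45 = 1.11 m.
- Assumed f of 10% to 50% and d of 10 to 50 m: from 0.10 × 10 = 1 m to 0.50 × 50 = 25 m. A middle case is 0.20 × 20 = 4 m.

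For scale, the plan's clinically meaningful change is 19 to 22 m.

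**6. Could the significance conclusion change?** The only stated criterion is two-sided alpha 0.05. Take the plan's pilot gain of 57 m and treat its ± 60 m as the SD of change. SE = 60/√45 = 8.94 m, t(44) = 2.015, half-width 18.0 m and lower limit 39.0 m. Bringing that limit to zero needs about 39.0 × 45 ≈ 1,754 person-metres of downward shift: 1,754/50 = 35.1, so 36 of 45 people at 50 m each. At 30 m each, all 45 would not suffice (57 − 30 − 18.0 = 9.0 m).

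The pilot figures in yards give a smaller gain: 418 − 363 = 55 yards, × 0.9144 = 50.3 m. The lower limit is then 32.3 m, and 32.3 × 45 ≈ 1,452, so 30 people at 50 m; again 45 at 30 m would not suffice (50.3 − 30 − 18.0 = 2.3 m). These counts hold the SD at 60 m. Adding d²p(1 − p) × 45/44 to the variance, with p the shifted share, lowers them to 35 and 28.

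**The case for a change.** The best case for a change is that returners are foreseen, the design has no control group, and a sentence settling the matter in advance would cost almost nothing. A baseline left open can in principle be chosen after the data are seen, and at the far end of the assumed range the shift of 25 m exceeds the plan's clinically meaningful change. Direction matters too: if function fell during the pause, a re-entry baseline would count recovery of lost function as gain, whereas the pre-pandemic baseline would understate the programme's effect.

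Most of this stands as a description of the gap. It does not show an error. The 25 m figure needs half of those analysed to be affected returners with a 50 m difference each, and nothing in the documents supports either value; drift could be zero or go either way. The remedy would not settle the substance either, since both baselines have a defensible rationale and a drawback, and the choice would still be the sponsor's. The 2021 consent form and letter to subjects are listed but cannot be read here, and may say which tests are repeated.

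A related worry is that some returners were first assigned to exercise alone. The documents never say so; it is inferred from leftover two-group wording. The intention-to-treat principle already bears on how such people would be labelled.

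**Conclusion.** No change to the plan follows. The documents leave out a detail for one subgroup, and an analyst can fill it sensibly. Visits indexed by months of intervention point to a clock that runs on programme time. A returner who already has a 3-month pair keeps it. For the others, one baseline visit serves walk, strength and body composition alike, because Phase 2 collects body composition and physical function as one set of tests. Where scans are not repeated at re-entry, those people drop out of the aim 2 change regressions or are imputed. Showing the primary result with and without returners is ordinary reporting practice.

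The size is unknown, not shown to be negligible: 0.67 to 1.11 m per affected person in a mean of 45, on an assumed 30 to 50 m difference between baselines. On the pilot gains, the significance conclusion would survive unless some 28 to 36 of 45 people were each shifted down by 50 m. That rests on 45 completers, reading ± 60 m as the SD of change, and a true gain close to the pilot's; a smaller gain would be less robust.
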